9.4.2 ANALYSIS OF THE PRIMARY ENDPOINT(S)

- a) Administrative Claims
 - a. Outcome variables of interest
 - i. Opioid misuse- “Overlapping Rx” OR “Multiple Rx on same day, different provider”
 - ii. Chronic opioid use- more than 60 days supply in a 90 day window
 - iii. Opioid use disorder- ICD-10 T40* (Poisoning by, adverse effect of and underdosing of narcotics and psychodysleptics) &/Or ICD-10 F11* (opioid related disorders) &/or prescribed MAT (Drug name contained “methadone” or “buprenorphine”; picks up buprenorphine, suboxone, zubsolv, naltrexone, methadone, narcan, and vivitrol)
 - b. Compute statistics for baseline period (06/01/2019-05/31/2022) and follow-up (06/01/2022-05/31-2023)

- i. Categorical data will be presented as N (%), continuous data as median (25th, 75th %tile)
- c. Run comparisons between baseline and follow-up time points
 - i. Comparisons involving two categorical variables will be made using Fisher's exact test
 - ii. Comparisons involving a continuous variable and a categorical variable will be made using Wilcoxon Rank Sum test or Kruskal Wallis test

b) Worker Survey

- a. Outcome variable of interest
 - i. Opioid misuse- Participant responded yes to one of the following two questions:
 - 1. Did you use the pain medication more than prescribed, or for a longer period than prescribed? [pnmed_longer]x
 - 2. Have you used prescription pain medications that were prescribed to someone else? [pnmed_othersrx]x
 - b. Compute the change at 6 months post-intervention (change of opioid misusep) of group-level data collected from groups of health

All endpoints are independent outcomes.

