 - 1. Serial prescriptions (most common scenario)
 - a. Start with all opioid first fills (including unlinked and linked with medical claims, using the process above)

- b. Arrange all fills by UID and fill date
 - c. Assign fills to claims that 1) occur after a claim with a linked opioid fill, and 2) opioid fill date is no more than 30 days after previous fill runout date (fill date + days supply)
2. Refills specified in the pharmacy data
 - a. Join opioid refills (from 1b above) with the first fills using prescription identifier ("RXNUM").
 - b. Assign claim information from first fills to linked refills

Variable definitions

- e. Opioid-related variables. These variables were generated using information from the medical claims and pharmacy fill data from the health fund and the CDC opioid file "CDC opioid NDC_oral MME conversion_update_2020.xlsx". The CDC file was merged with health fund pharmacy fill data on NDC
 - i. Medication assisted treatment (MAT): Drug name contained "methadone" or "buprenorphine" in either file or drug description was "ANTIDOTES AND SPECIFIC ANTAGONISTS" in the pharmacy fill file
 1. This strategy picks up buprenorphine, suboxone, zubsolv, naltrexone, methadone, narcan, and vivitrol
 - ii. Opioid: pharmacy class was "opioid" in the CDC file, and the drug was not already identified as MAT (see above)
 - iii. OUD: ever ICD-10 code "T40x" or "F11x" on a medical claim or identified as MAT (see above)
 - iv. Days supply > 7 days: based on "days supply" as provided in fill data
 - v. MME/day: Instructions for calculation are in CDC file. Formula is "strength per unit" * "average quantity per day" * "MME conversion factor"
 - vi. Overlapping Rx: Date opioid fill is within previous days supply (current fill date < previous fill date + days supply)
 1. When the previous prescription is a "short course" (the prescription window is encompassed by prescription before it), the prescription before the short course is used in evaluation
 - vii. Chronic use (>60 days supply in a 90 day window)
 1. For each worker time is divided into 90 day "cycles", starting with the date of the first opioid fill
 2. Days supply is totaled within the 90 day cycle
 3. If the individual had opioid fills later than 90 days after the first fill, a new cycle is started and the process starts over
 4. When workers have multiple opioids filled on the same day, use the longest days supply in calculations

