 5. Indicator variable for total days supply in a cycle > 60 for any given cycle
 - viii. Multiple Rx in a single visit: multiple Rx filled on the same day and NPI is the same between fills

- ix. Multiple Rx on same day, different provider: multiple Rx filled on the same day and NPI between Rx different. Could indicate doctor shopping
- x. Misuse: “Overlapping Rx” OR “Multiple Rx on same day, different provider”
- f. Diagnoses. These variables were generated from information in the medical (i.e diagnosis and procedure) claims. Diagnoses are assessed at the claim level, and “rolled up” to the worker (i.e, has worker ever had a diagnosis for X)
 - i. MSD surgery: CPT codes 20005-21010; 21500-22900; 62263-63746; 64400-64999
 - ii. Acute MSD injury: ICD-10 codes ranging S00-T14
 - iii. Chronic MSD: ICD-10 codes M.x, G54-G57
 - iv. Recurring acute injury. Acute MSD injuries that occur across multiple claims are recoded as “recurring injuries”. These are combined with chronic MSD for our purposes
 - 1. ICD-10 codes for acute MSD injuries are identified on a given claim (see above)
 - 2. If the same ICD-10 code occurred on a previous claim more than 30 days before the claim in question, the acute MSD injury is recoded as “recurring injury” on the claim in question and will no longer be counted as an acute MSD injury
 - 3. Using this method, the first occurrence of a given acute MSD injury ICD10 code will be left as “acute MSD injury”
 - v. Other diagnosis: Claims that do not fit into i-iv above are coded as “other Dx”
 - vi. Acuity: claims can have multiple diagnoses associated with them. Acuity is assigned as follows, regardless of other diagnoses associated with the claim: MSD surgery, Acute MSD Injury, recurring injury or chronic MSD, other diagnoses.
 - 1. So if a claim had codes for both MSD surgery and chronic MSD, the acuity is assigned to MSD surgery
- g. Description of the study sample [all data are in “claims eligibility_20230213.docx”, unless otherwise noted]
 - i. Demographics and worker characteristics
 - 1. Gender
 - 2. Age in 2022
 - 3. Plan status (Active, COBRA, etc)
 - 4. Time worker eligible for benefits during study period
 - 5. Gaps in eligibility
 - ii. Plan utilization
 - 1. Proportion of workers with a health claim, pharmacy claim, overlap of these
 - iii. Distribution of diagnoses based on original order of acuity
 - iv. Diagnoses. Number of workers with:
 - 1. MSD surgery
 - 2. Acute MSD injury

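### Chronic opioid use is defined on a 90-day window but coded in 90-day cycles from the first fill, so a worker whose supply is split by a cycle boundary can be missed

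*Combined protocol and SAP*

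**What the plan says.** Section 9.4.2 lists three claims outcomes, the second being "Chronic opioid use- more than 60 days supply in a 90 day window". Section 9.4.1 calls all three claims outcomes primary. The descriptive tables listed in the data-management appendix repeat the same threshold for a 90-day period.

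Item e.vii of that appendix (Data management of Administrative Health Claims and Worker Surveys) gives the coding steps:

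- Cutting of time: "For each worker time is divided into 90 day" cycles, "starting with the date of the first opioid fill".
- Accumulation: "Days supply is totaled within the 90 day cycle".
- Restart: "If the individual had opioid fills later than 90 days after the first fill, a new cycle is started and the process starts over".
- Same-day fills: "When workers have multiple opioids filled on the same day, use the longest days supply in calculations".
- Flag: "Indicator variable for total days supply in a cycle > 60 for any given cycle".

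No rolling window, overlap between cycles or carry-over of supply is described. The restart step does not say whether the new cycle begins at day 90 or at the next fill. Nothing says what happens to a cycle in progress on 06/01/2022, where Section 9.4.2 separates baseline from follow-up.

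**The concern.** The definition speaks of a window and the coding uses blocks whose position is set by the first fill. The two agree only when the worker's supply falls conveniently within a block. Otherwise two workers with the same sustained exposure can be classified differently because one of them filled a short prescription some weeks earlier.

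The outcome is in the primary claims analysis, is to be compared between baseline and follow-up, and the study's data are meant to inform power calculations for a later trial. A classification that depends on cycle position rather than exposure weakens both uses. Two programmers following the restart step could also report different counts.

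**Working it through.** The plan gives no expected chronic-use rate or fill distribution, so there is no figure to reproduce. The check applies the rule as written to constructed fill histories.

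**Inputs from the documents:** 90-day cycles from the first fill; flag if a cycle total exceeds 60. **Assumptions:** each fill's whole days' supply is credited to the cycle containing its fill date; fill patterns are illustrative.

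**Two restart readings:** (a) a fixed grid, with cycles covering days 0-89, 90-179 and so on; (b) a cycle re-anchored at the next fill after the previous cycle ends.

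**One worker.** Fills on day 0 (5 days) and on days 75, 105 and 135 (30 days each).

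| Rule | Totals | Chronic? |
|---|---|---|
| (a) Fixed grid | 5 + 30 = 35; 30 + 30 = 60 | No |
| (b) Re-anchored at day 105 | 35; 60 | No |
| 90 days from day 75 | 30 + 30 + 30 = 90 | Yes |
| Cycle rule without the 5-day fill | 90 in one cycle | Yes |

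**Run starting in the first cycle.** One first fill of 3-10 days, then three 30-day fills starting on day u.

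- u before day 30: all three fills fall in cycle 1, total at least 90, flagged.
- u from 30 to 59: two fills plus the short one, at least 60 + 3 = 63, flagged.
- u from 60 to 89: one fill plus the short one, at most 40, then 60 in cycle 2; missed.

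That is 30 start days out of 87 (3-day first fill), 85 (5-day) or 80 (10-day): 34.5%, 35.3% and 37.5%. If a fill on exactly day 90 still belongs to cycle 1, as the words of the restart step suggest, u = 60 is caught under reading (b). Then 29 are missed: 29/87 = 33.3% to 29/80 = 36.3%. The range is about 33-38%. Summing over the 90 days from each fill misses none.

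**Run starting in a later cycle** (days 90-719, 630 start days).

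- Three fills, fixed grid: a start in days 0-29 of a cycle is flagged; days 30-59 give 60 and 30; days 60-89 give 30 and 60. Missed: 60/90 = 67% (420 of 630).
- Four fills, fixed grid: only starts in days 30-59 are missed (60 and 60). 30/90 = 33%.
- Five fills (150 days), fixed grid: every start puts three fills, 90 days, in some cycle. Missed: 0%.
- Re-anchored: the run's first fill opens its own cycle, so almost none are missed (at most 1 of 630 for three fills, none for four).

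**Run that is the worker's first.** For equal fills of 1-60 days and gap-free runs up to 200 days, none are missed.

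**Sensitivity to the crediting assumption.** Suppose supply is split day by day at a fixed-grid boundary, with a 5-day first fill. Cycle 1 then holds 5 + (90 - u) and cycle 2 holds u. Both are at most 60 when u is 35 to 60, which is 26 of 85 start days (31%). Different start days are lost, but the problem remains.

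**The case against.** The strongest reply is that the plan never says rolling, or any 90 days. The appendix repeats the definition as its heading and then spells it out, so the cycles could be taken as the definition. It is true that the wording is under-specified. It does not rescue the rule: a worker with 90 days' supply inside 90 days meets the definition on any ordinary reading, and the same run is classified differently once an earlier short fill is added.

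Several stronger readings are tempting, and the documents do not support them.

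- A reader might infer that every continuous user who crosses a boundary is lost. Crossing is not enough; every cycle's share must be 60 or less. Sustained 30-day-fill users are caught.
- A reader might take 33-38% as the share of chronic users missed. It is a share of start days under one assumed pattern. Spread over 720 start days after a 5-day first fill, 90-day runs are missed for 62.5% on the fixed grid but 4% when re-anchored. None of these is an estimate for this trial.
- A reader might infer that cycles run across 06/01/2022. The documents are silent, and the appendix's inclusion rule names only 6/1/2019-5/31/2022 as its study period.
- A reader might infer a biased pre-post change. Nothing shows that misses differ between periods.

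The objection on importance partly stands. The endpoint statements in Sections 1, 3 and 9.1 name misuse, opioid use disorder and overdose rather than chronic use. Section 9.1 plans no formal hypothesis testing, and Section 3 says the study is not powered for changes in outcomes.

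**Conclusion.** The point holds in limited form. The coding does not deliver the window definition in Section 9.4.2 and can miss workers who meet it, under both readings of the restart step. With 30-day fills the exposed group is runs of about 90 days that follow an earlier fill, extending to 120 days on a fixed grid. Other fill lengths shift these limits. The number affected cannot be estimated from the documents, because it depends on the fill patterns and on the restart rule, which is not fixed.

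The correction is worth making because the outcome sits in the primary claims analysis and the data needed are already requested. It does not threaten the feasibility conclusions.

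**What to change.** Replace the cycle steps in item e.vii with this rule: for each opioid fill, sum days' supply over the 90 days starting at that fill, keep the same-day rule, and flag the worker if any such window exceeds 60.

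State one rule for windows that span 06/01/2022 and apply it identically to baseline and follow-up. Either assign the window to the period in which it starts, or truncate at the boundary and accept that spanning runs may be missed. Truncation has a real cost: 30-day fills on 1 May, 31 May and 30 June 2022 give 60 in baseline and 30 in follow-up, so that run would go unflagged.

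If cycles are kept, Section 9.4.2 should define the outcome in cycles, and the appendix should say where each new cycle starts and whether cycles reset on 06/01/2022. The misses shown above would then remain.

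The cost is a small code change and a sentence or two in the appendix. Reported chronic use may rise slightly.

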20.1 ABBREVIATIONS AND SPECIAL TERMS

AE	Adverse Event
CFR	Code of Federal Regulations
CDC	Centers for Disease Control and Prevention
COC	Certificate of Confidentiality
COBRA	Consolidated Omnibus Budget Reconciliation Act
CPT	Current Procedural Terminology
DHHS	Department of Health and Human Services
DSMB	Data Safety Monitoring Board
Dx	Diagnosis
FDA	Food and Drug Administration

HIPAA	Health Insurance Portability and Accountability Act
ICD-10	International Classification of Diseases, Tenth Edition
IRB	Institutional Review Board
MAT	Medication Assisted Treatment
MME	Morphine Milligram Equivalents
MSD	Musculoskeletal Disorder
NDC	National Drug Code
NIDA	National Institute on Drug Abuse
NIH	National Institutes of Health
OHRP	Office for Human Research Protections
OUD	Opioid Use Disorder
PI	Principal Investigator
QA	Quality Assurance
QC	Quality Control
Rx	Prescription
SAE	Serious Adverse Event
SAP	Statistical Analysis Plan
UID	Union member ID
UP	Unanticipated Problem
US	United States

20.2 PROTOCOL AMENDMENT HISTORY

There were no changes made to the IRB-approved versions of the protocol.

